Study Title: *Clinical Study of the CO₂RE Laser Device for Treatment of Vulvar Lichen Sclerosus*

Protocol Number: DHF25211

IRB Revision Date: February 19, 2019

NCT#: NCT04148651

Study Type: Prospective Clinical Study

Device: *CO₂RE Laser*

Sponsored By: Candela Corporation
[name]
[name]

This document is the property of **Candela Corporation** No part of this document may be reproduced, stored in retrieval system, or transmitted in any form or any means, electronic, mechanical, photocopying, recording or otherwise without prior written permission from **Candela Corporation**.

TABLE 1- STUDY SYNOPSIS

Short study name	Vulvar Lichen Sclerosus Treatment with CO ₂ RE			
Proprietary name	Syneron Candela CO ₂ RE Laser			
Intended Use	The CO ₂ RE laser system is a fractional CO ₂ laser that is FDA-cleared under a 510(k) K151655 for laser incision, excision, ablation and/or vaporization and of soft tissue in gynecology (GYN).			
Design	Prospective, non-randomized, single group assignment, interventional clinical trial			
Study Population	Up to 45 female subjects from up to four investigational sites, age 18-80 years			
Sites and Investigators	Up to 4 investigational sites			
Treatment Duration	
Eligible subjects, with a diagnosis of vulvar lichen sclerosus (VLS) supported by histologic findings on biopsy and/or clinical signs on physical examination and recalcitrant to mid- to high-potency steroid therapy, will undergo up to 5 treatments at 4±1-week intervals to the vulva with the CO₂RE device and External Intima disposable handpiece. Up to 10 subjects will have a biopsy taken at the baseline visit, at the 6-week follow-up and at the 6-month follow-up to evaluate histological markers compared to pre-treatment biopsy findings.
 
A 1 week ± 2 days post first treatment phone call by a study nurse for safety evaluation will be performed.
 
Subjects will return for 4 follow-up (FU) visits: at 6 weeks, 3 months, 6 months and 12 months after the final treatment.
 
Methodology described in protocol to evaluate efficacy of treatments will be carried out at each visit at the clinic.
			
Primary Objective	Evaluate the efficacy of a series of CO ₂ RE treatments to improve the symptoms, clinical signs, and architectural changes associated with vulvar lichen sclerosus, at 6 weeks, 3 months, 6 months and 12 months after the final treatment.			

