Change from baseline in presence and severity of symptoms (5-point severity scale), clinical signs (3-point severity scale) and architectural changes (3-point severity scale) at the 6-week, 3-month, 6-month and 12-month follow-up visits. (**Appendices I & II**).

Secondary Safety Endpoints

Evaluate the safety of the treatment:

1. Clinical evaluation of treated area at each study visit. Clinical photography will be performed for study documentation (**Appendix IV**).
2. Pain/discomfort level using a 10-point Numerical Scale Response (NSR) after each treatment (**Appendix V**).
3. Number, severity and type of adverse events recorded throughout course of the study.
4. 1 week ± 2 days post first treatment safety phone call (review of 1-week patient diary) – (**Appendix VI**).

Secondary Efficacy Endpoints

1. Sexual function, using the Female Sexual Function Index (**Appendix III**), at baseline and at the 3-month and 6-month follow-ups. *An overall score ≤ 26.55 is classified as Female Sexual Disorder (FSD).*¹⁵
2. Histological signs (degree of hyperkeratosis, epidermal atrophy and dermal inflammation) at baseline and at 6 weeks and 6 months after the final treatment.
3. Subject satisfaction, using a 5-point Likert scale (-2=very dissatisfied; 2=Very satisfied), will be assessed at the 6-week, 3-month, 6-month and 12-month follow-up visits (**Appendix VII**).

SUBJECT POPULATION

Up to 45 female subjects who meet the following inclusion / exclusion criteria may be enrolled.

Subject Withdrawal and Replacement

Subjects enrolled in the study can discontinue their participation at any time for any reason without prejudice or reduction in the quality of their medical care. The investigator or sponsor can terminate a subject's participation in this study to protect the subject's health or if the subject fails to follow directions resulting in noncompliance to study procedures. Subjects who withdraw or are terminated from the study may be replaced to allow up to 45 subjects to complete the study. Subjects who fail to complete the treatment will be replaced and will not be evaluable.

Inclusion Criteria

1. Able to read, understand and sign informed consent for study participation;
2. Female subjects with age 18-80 years;
3. Biopsy demonstrates biopsy-proven lichen sclerosus and/or there are characteristic changes for vulvar lichen sclerosus on physical examination;

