Table 2. Study Measurements

Assessment	When to conduct	Method
Complete the Inform Consent form and Eligibility Screening and Medical History	During the screening visit / prior to the 1 st treatment	Physician or staff will complete the form with the study subject
PAP smear if not up-to-date (within 3 years according to ACOG guidelines)		Patient should provide lab results of up-to-date normal cell cytology
Urine pregnancy test for women capable of becoming pregnant		Patient should have a negative pregnancy test
Gynecological exam		Physician will examine the vulvar and vaginal area for any signs of active infection or atypical nevi
Vulvar biopsy of treatment area (optional)	Prior to the 1 st treatment and at the 6-week and 6-month follow-ups	Biopsies will be obtained from up to 10 subjects to conduct histological assessment. Lab reports will be provided to show changes in markers compared to baseline.
Subject assessment of symptoms	
 • Baseline or pre-Tx. 1 • At the 6-week, 3-month, 6-month and 12-month follow-up visits 	Subjects will complete the Symptom Severity Questionnaire, according to the pre-defined scales (Appendix I)
Physician assessment	
 • Baseline or pre-Tx. 1 • Prior to treatments • At the 6-week, 3-month, 6-month and 12-month follow-up visits 	Physician will assess clinical signs associated with VLS, according to the pre-defined scales (Appendix II)
Subject assessment of sexual function	
 • Baseline or pre-Tx. 1 • At the 3-month and 6-month follow-up visits 	Subjects will complete the Female Sexual Function Index (FSFI) – Appendix III
Clinical evaluation and photographs of treated area	
 • Baseline or pre-Tx. 1 • Prior to treatments • At the 6-week, 3-month, 6-month and 12-month follow-up visits 	Physician will evaluate the treatment area. Physician or staff will take photographs of the treatment area (Appendix IV)
Treatment pain assessment	Immediately after each treatment	NSR Scale (Appendix V)
Subject 1-week daily diary - reviewed at the 1wk FU after the first treatment	The daily diary will be provided at the 1 st treatment visit and reviewed by phone during the 1-week safety evaluation	Subjects will be requested to complete a daily diary with data regarding their comfort, AE, and activity (7 days of follow-up post 1st treatment) – Appendix VI

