The biopsy specimen should be taken from the area of the vulva or peri-anal skin that clinically appears to have the most active or developed VLS changes. A 3-mm or 4-mm punch can be used in most cases. A 3-mm punch biopsy is generally thought to be the smallest size that will provide an adequate sample of tissue for pathologic analysis. However, certain locations where there is little subcutaneous adipose tissue, such as the labia minora and the clitoral hood, may be best sampled by scissor snip technique. The chosen location and biopsy technique should be based on the provider's best judgment of potential histological change as well as patient comfort and healing. Adjacent skin of the same area should be sampled for post-treatment follow-up biopsies.

Mark the biopsy site with surgical skin marker and photograph the marked location. To minimize patient discomfort, apply topical anesthetic prior to injecting local anesthetic. Then, draw 1ml of 1% lidocaine with 1:100,000 epinephrine into a 1ml syringe. Slowly inject the anesthetic with a 30-gauge needle. While this amount of local anesthetic is adequate for the majority of patients, additional anesthetic can be injected as clinically warranted. When anesthetizing the area, insert the needle and withdraw the plunger to decrease the chance that injection occurs into a vessel. Inject slowly at the base of and underneath the lesion, injecting enough to create a wheal. If possible, only penetrate the skin once. The wheal should be larger than the biopsy instrument that will be used. Adequate anesthesia for the procedure should be present in 1-2 minutes. Test for appropriate anesthesia prior to making any incision. As in most clinical situations, biopsy is performed shortly after injection.

Once an adequate biopsy sample has been excised, the specimen should be placed carefully in a fixative solution, such as 10% formalin. Confirm that the sample is in the container after closing the lid. The tissue should be sent to pathology along with the properly completed pathology forms. Insurance information should not be included on the form, as study subjects will not be billed for biopsies. Patient Initials and Subject Code should be included on the specimen labels (i.e. 001_AMK).

Hemostasis may be achieved with pressure only for small specimens. In addition to pressure, bleeding also may be controlled with suture or gel foam for punch biopsies or with aluminum chloride or silver nitrate for scissor snip biopsies.

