All data will be recorded on Case Report Forms (CRFs) or transcribed from source documentation, where applicable (i.e. lab reports). The site will be monitored by Syneron Candela staff or designees to assure adherence to the clinical trial requirements, subject safety, protocol procedures, and for data accuracy. The Case Report Forms and images will be reviewed and retrieved during the monitoring visit. All source documentation will remain in the subject's files at the site.

Review and Analysis of all data collected will be conducted by the Sponsor or designee as described for this protocol with the following data:

Demography and Baseline Measurements

Demographic and baseline/screening measurements (e.g., age, weight, clinical VLS signs and digital images) will be collected and descriptively presented.

Treatment Visits

Clinical VLS signs as assessed by the study investigator, photographs of the treated region, and NSR scores will be collected and compared to baseline to assess efficacy and safety. Any potential adverse events will be documented.

Follow-up Visit Measurements

Follow-up measurements, efficacy and satisfaction assessment scores, and digital images will be used for comparative measurements with their respective data at baseline. Primary endpoints will be evaluated at the 6-week, 3-month, 6-month and 12-month follow-up visit.

Safety

Safety of device procedure will be evaluated throughout the study. Any side effects to the treated area will be reported by the subject, the study investigator and the research staff. The occurrence and severity of all complications from the start of the study will be recorded.

ADVERSE EVENTS (AE)

An adverse event (AE) is any adverse change in health or side effect that occurs in a study participant during their participation in the study.

Anticipated Adverse Effects

An adverse event (AE) is any undesired clinical occurrence in a study subject as indicated by signs, symptoms, illnesses, events that develop or worsen in severity in association with the study when deemed by the Investigator to be related to use of the device or study procedures.

Anticipated post-treatment adverse effects which could result from the CO₂RE treatment include pain, swelling, bruising (ecchymosis), blistering, burn, and infection.

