APPENDIX IV – PHOTOGRAPHY GUIDELINES

At each time point (before the treatments and at the follow-up visits), photographs of the treated area should be taken in a standardized manner.

- Photographs should be taken in a private room or area of the clinic under controlled conditions, including the distance from the camera to the subject, height of the camera, background, camera positioning, subject's positioning and lighting in order to achieve high quality before & after sets.
- For consistency purposes, the same person should ideally take all study photographs, especially per subject.
- Small plain labels (with the date, subject ID, subject initials, Investigator name, and identity of the specific area photographed, if necessary) should be placed in the same location within each frame at each photography timepoint. The presence of the label should not impair the photo's desired effect or obscure the treated area.
- The digital files should be labeled in a standardized manner (subject number, subject initials, study visit). For example: 001JS_Tx1, 001JS_FU1, etc.

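### Lab reports are to show histological change from baseline, no visit-masked reading is provided for, and the example specimen label does not distinguish visits

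*Protocol*

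**What the plan says.** The histology endpoint is listed under Secondary Efficacy Endpoints: "Histological signs (degree of hyperkeratosis, epidermal atrophy and dermal inflammation) at baseline and at 6 weeks and 6 months after the final treatment". Biopsy is optional and limited to at most 10 of the up to 45 subjects.

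Four instructions bear on how the specimens are identified and read:

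- Table 2 (Study Measurements), vulvar biopsy row, on what the laboratory delivers: "Lab reports will be provided to show changes in markers compared to baseline".
- Vulvar Biopsy Procedure, on labelling: "Patient Initials and Subject Code should be included on the specimen labels (i.e. 001_AMK".
- The same section, on paperwork: "The tissue should be sent to pathology along with the properly completed pathology forms". The fields of that form are not listed.
- Data Analysis, Recording, on how results reach the database and who analyses them: "All data will be recorded on Case Report Forms (CRFs) or transcribed from source documentation, where applicable (i.e. lab reports", and "Review and Analysis of all data collected will be conducted by the Sponsor or designee as described for this protocol".

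For photographs the protocol is more specific. Appendix IV states "The digital files should be labeled in a standardized manner (subject number, subject initials, study visit", and the label in the photograph also carries the date.

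No section says that the histology reader is masked to visit, that slides are coded, or that one reader grades all of a woman's specimens.

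**The concern.** The endpoint is the degree of three features, judged by eye. The protocol gives no grading scale for them, unlike the symptoms and signs in Appendices I and II. Judgements of this kind are open to expectation when the reader knows that a specimen was taken after treatment.

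The trial is single-arm and open. Symptoms, sexual function and satisfaction are self-reported, and the study investigator scores the clinical signs. Slides, by contrast, can readily be coded and read without knowledge of the visit, and up to 10 women undergo three biopsies each to supply them. As written, Table 2 points the other way: a report that shows change from baseline invites a reader who knows which specimen is the baseline.

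The label is a separate and lesser matter. In the form exemplified it would be the same on all three of a woman's specimens, so it serves neither as a masking code nor as a unique specimen identifier.

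**Working it through.** The protocol gives no sample size, SD, test or alpha for histology, so there is no figure of its own to reproduce. The check is mainly a reading of the text; the arithmetic after it is illustrative.

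**Reading the text**

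1. *Who derives the change?* The Table 2 sentence is passive. It may mean that the lab compares the specimens, which requires knowing which is baseline. It may also mean that separate per-specimen reports are later compared. The Recording section treats lab reports as source documents and assigns analysis to the sponsor or a designee, so the second reading is possible. The protocol does not choose.
2. *Does the label identify the specimen?* The example `001_AMK` holds a subject code and initials only. The rule lists items to include and does not exclude others, and a pathology form accompanies the tissue. So the prescribed label does not distinguish visits, but a visit or date elsewhere is not ruled out.
3. *Does the label unmask the reader?* No. A label without the visit tends, if anything, to hide it. Any unmasking comes from the Table 2 instruction or from the form.
4. *Is masking provided for anywhere?* No.

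**Size of an expectation shift (assumptions, not protocol figures)**

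Inputs: n = 10 (the protocol's maximum). Assumed: no true effect, a mean reading shift b, an SD of change s, and a two-sided 5% paired t-test with 9 df (critical value 2.262). The noncentrality is δ = b√n / s. The false-positive rate is P(|T| > 2.262), where T is noncentral t with 9 df and noncentrality δ.

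| Shift b (grade) | SD s | δ | False-positive rate |
|---|---|---|---|
| 0.25 | 0.7 | 1.13 | 0.173 |
| 0.25 | 0.8 | 0.99 | 0.144 |
| 0.25 | 1.0 | 0.79 | 0.109 |
| 0.50 | 0.7 | 2.26 | 0.522 |
| 0.50 | 0.8 | 1.98 | 0.423 |
| 0.50 | 1.0 | 1.58 | 0.293 |

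Up to 10 × 3 = 30 specimens would be read, of which 20 are post-treatment.

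**Size of a specimen mix-up (secondary)**

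Suppose every woman has the same true change d, and baseline and follow-up are exchanged in k of n women. The mean change is then d(1 − 2k/n): with n = 10, 0.8d for one swap and 0.6d for two. Of the three possible pairwise swaps within a woman, the two that involve baseline reverse the sign of one change and distort the other. A 6-week/6-month swap reverses neither.

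The protocol says of subjects that they "will undergo up to 5 treatments at 4±1-week intervals". With all five treatments and the baseline biopsy at the first, the gap to the 6-week visit is about 4×4 + 6 = 22 weeks (range 4×3 + 4 = 16 to 4×5 + 8 = 28). The gap from the 6-week to the 6-month visit is about 20 weeks (16 to 24). At such distances a mix-up is plausible mainly if specimens are stored and read together, which the protocol does not say.

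**The case against.** The strongest reply is that this is an omission of laboratory detail. Reader masking, slide coding and form fields could sit in a lab manual, and Table 2 is loosely worded rather than wrong. Per-specimen reports with change computed by the sponsor would satisfy it. The endpoint is optional, secondary and confined to at most 10 women.

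Part of this stands. A reader might infer from Table 2 that the pathologist must personally report change and therefore must be unmasked. The sentence does not say so, and the Recording section leaves room for the sponsor to derive it. A reader might also infer that a woman's three specimens necessarily bear one identical label. The rule sets a minimum, and the accompanying form may carry the visit or date. Nor can a label without the visit be what removes masking. The swap argument is speculative, and its effect, a pull towards no change, runs opposite to the expectation bias that is the main worry. The false-positive rates show only what an assumed bias does to an assumed test.

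What does not stand is the suggestion that nothing is fixed badly. The protocol does prescribe what the lab reports should show and what the label should contain. Someone who follows both instructions as written gets no masked reading of a subjective endpoint. That the text can also be followed in a harmless way is a reason to settle the wording.

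**Conclusion.** The point holds in limited form. The protocol asks for lab reports that show change from baseline in three subjectively graded signs, does not provide for visit-masked reading, and gives a label example that does not separate baseline, 6-week and 6-month specimens. This leaves the histology endpoint exposed to expectation bias in an open single-arm trial.

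It does not establish that the readings will be unmasked, that specimens will lack identification, or that any will be exchanged. The quantified inflation rests wholly on the assumed shifts, SDs and test. The primary endpoint is not affected. This is a cheap improvement worth making, with masking as the main reason and specimen identity as a secondary one.

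**What to change.** - In Vulvar Biopsy Procedure, require a unique code on each specimen that does not reveal the visit, with the key linking code to subject and visit held at the site and kept from the reader.
- State that the pathologist grades hyperkeratosis, epidermal atrophy and dermal inflammation on each coded specimen without visit information.
- Replace the Table 2 sentence with one saying that lab reports will give a grade per coded specimen and that change from baseline is computed afterwards by the analyst.
- Where feasible, have one reader grade all of a woman's specimens. This should be optional: with up to four sites, a single reader or a single reading session is not shown to be free.

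The cost is a code log and a small change to the pathology form and workflow, with edits to two places in the protocol. The required steps need no additional biopsy or reader. Any diagnostic report needed clinically can still be issued at once, separately from the research grading.

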Contemporary VLS treatment modalities suffer from dependence on long-term patient compliance and high recurrence rates. The fractional carbon dioxide laser (CO₂) has been applied to treat skin disorders⁷ and to induce vaginal rejuvenation⁸, reconstitute normal vaginal flora⁹ and to drive collagenogenesis tissue remodelling.¹⁰ Although topical steroids are the gold standard treatment for VLS, fractional CO₂ resurfacing was successful in achieving remission for severe, hyperkeratotic VLS not responding to super-potent topical corticosteroids. In these patients, VLS was subsequently able to be maintained with topical corticosteroid treatment.¹⁰

The histological changes and relief of vaginal symptoms, such as itching and dryness, elicited with fractional CO₂ technology justify testing it as an alternative and/or adjunctive treatment for VLS. This clinical research will evaluate treatment efficacy of the CO₂RE CO₂ laser device with the External Intima fractional handpiece for improving the clinical signs of VLS and relieving symptoms associated with this condition.

CO₂RE Device Description

The CO₂RE laser system (Figure 1) utilizes a sealed-off, metal carbon dioxide gas tube that is radiofrequency (RF)-excited and air-cooled, emitting light at a wavelength of 10.6 µm with

programmable pulse duration and frequency. The system has a programmable 2-axis scanning laser beam device that allows the physician to select the skin area coverage from a selection of predetermined patterns in different sizes based on the skin area to be treated. The versatility of the fractional CO₂RE system enables precise, effective and simultaneous treatment of the skin's surface in the middle and deep dermal levels. The CO₂RE system consists of a treatment component and an internal control component. The treatment component consists of the laser delivery handpiece. A computer with a touch screen keyboard also provides controls for the fractionated delivery of the 10.6 μ m beam.

Figure 1: CO₂RE device

In this study, the external fractional handpiece (Figure 2) will be used to perform treatments to the vulvar area affected by lichen sclerosus.

Figure 2: CO₂RE Intima External Handpiece

INTENDED USE IN GYNECOLOGY

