5. Affected areas of the vulva (vestibule, introitus, medial labial majora, intralabial sulcus, labia minora and clitoral hood) will be treated.
6. Subject should remove their pants and underwear.
7. Prepare the CO₂RE device for the treatment procedure, including cleaning the handpiece's reflecting mirror (wiped and dried well with ≥70% alcohol).
8. Turn the CO₂RE device on and select the treatment parameters.

Treatment

1. The distal part of the External handpiece should be clean and dry. The handpiece should be held perpendicular to and in close contact with the skin. In the same manner, the distal end of the handpiece should be moved to the designated spot.
2. Prior to treating the entire area, several test spots should be performed in a small section within the area to assess the skin for unwanted effects.
3. The choice of treatment settings should take into consideration the subject's skin type, tendency to bruise, and the specific anatomical location (vulva).
4. Set the CO₂RE treatment parameters according to investigator decision taking into consideration the necessary ablation depth (which is influenced from the amount of water in the vaginal tissue).
5. Single pass laser exposures will be performed at a Repeat Rate of 0.5 – 1 seconds, using the following parameters:

Deep Mode

- Core (mJ): 40 – 50
- Fractional Coverage: 3 – 5%
- Pattern size (mm): 7.8 X 7.8 (Square)

And/or

Fusion Mode

- Core (mJ): 40 – 70
- Pattern size (mm): ANY, except 7.8 X 7.8
- Ring Fluence (J/cm²): 46 – 87.3
- Fractional Coverage: 20 – 30%

6. Consider dialing down the energy or changing the fractional density if more than pinpoint bleeding occurs.
7. Do not use pulse stacking or more than a single pass.

8. Once the user has selected the laser operating parameters and had located the handpiece at the proper treatment area, he / she can use the footswitch to activate the laser treatment.

Immediately Post Treatment

1. The immediate responses, for the desired effect, are erythema, edema and a distinct stippled gray fractional epidermolysis pattern that aids in visualization of treatment progress. The treatment parameters and treatment response should be noted in the CRFs.
2. Subject will be given a pain (NSR) scale to record the pain level they felt during the treatment.

Post-treatment Instructions for Subject

Subject will be provided with the following instructions for care of the treated areas as described in the informed consent form.

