Following the first treatment:

1. Subjects will receive a daily diary, which they will be requested to complete, regarding their comfort and any adverse events for the 7-day period following treatment.

Following each treatment session

1. If the subject experiences itch or discomfort after treatment, ice packs may be applied to the treatment area.
2. Temporary erythema (redness) and edema (swelling), as well as heat and tightening sensations, may occur up to a few hours after the treatment. If the subject feels significant discomfort longer than a few hours, an over-the-counter pain medication such as Tylenol® (Acetaminophen) may be used. Nonsteroidal anti-inflammatory drugs (NSAID), such as aspirin, Ibuprofen (Advil, Motrin), naproxen (Aleve, Anaprox, Naprelan, Naprosyn), etc. should be avoided unless the patient does not experience symptomatic relief with or is contraindicated to acetaminophen.
3. On the evening after the treatment, subjects should wash the treated areas gently with lukewarm water and avoid very hot or cold water in these areas. Generally, subjects may use their regular cleanser after treatment, as long as these are not mechanical scrubs or exfoliants.
4. Subject should refrain from sexual activities for a period of 7 days.
5. Any pain, fever or unusual discharge should be immediately reported.

 Candela Corporation Confidential	Clinical Study of the CO₂RE Laser Device for Treatment of Vulvar Lichen Sclerosus				
	Protocol #	DHF25211	Rev. Date	February 19, 2019	Page 16 of 39

Follow-up Visits

1. All subjects will be requested to return to the clinic at the following time-points during the study to assess the clinical safety and performance of the device:
 - 6 weeks post last treatment – 6wk FU ± 2 weeks.
 - 3 months post last treatment – 3m FU ± 2 weeks.
 - 6 months post last treatment – 6m FU ± 2 weeks.
 - 12 months post last treatment – 12m FU ± 2 weeks.
2. At the follow-up visits, the following assessments will be performed, and data recorded:
 - Review changes in medication, medical history and AE, if applicable, from last visit.
 - Photographs of treated area.
 - Optional biopsy of treated area (6-week and 6-month follow-up only).
 - Subject assessment of symptom severity.
 - Investigator assessment of clinical signs.
 - Subject Satisfaction.

DATA ANALYSIS

Recording

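### The biopsy may be taken from peri-anal skin, which is not among the areas listed for laser treatment, although the protocol elsewhere calls it a biopsy of treated skin

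*Protocol*

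**What the plan says.** Five places in the Protocol bear on where the biopsy comes from and where the laser goes.

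- **Vulvar Biopsy Procedure.** The specimen should be "taken from the area of the vulva or peri-anal skin that clinically appears to have the most active or developed VLS changes". The choice of location is left to the provider's judgment of likely histological change, comfort and healing. For later samples, "Adjacent skin of the same area should be sampled for post-treatment follow-up biopsies".
- **Pre-Treatment Instructions, item 5.** "Affected areas of the vulva (vestibule, introitus, medial labial majora, intralabial sulcus, labia minora and clitoral hood) will be treated".
- **CO₂RE Device Description.** The external handpiece "will be used to perform treatments to the vulvar area affected by lichen sclerosus". The synopsis (Table 1, Treatment Duration) likewise describes treatment of the vulva.
- **Table 2, Study Measurements.** The assessment is named "Vulvar biopsy of treatment area (optional", and "Biopsies will be obtained from up to 10 subjects to conduct histological assessment".
- **Follow-up Visits, item 2.** "Optional biopsy of treated area (6-week and 6-month follow-up only".

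The samples feed the second of the Secondary Efficacy Endpoints: three histological signs at baseline, 6 weeks and 6 months.

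**The concern.** The section that tells the site how to choose the biopsy location permits skin that the treatment section does not list for lasering. Two shorter descriptions of the same biopsy assume that the skin is treated. Both cannot hold for a subject whose most developed disease is peri-anal.

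Because follow-up samples come from the same area, the baseline choice carries forward. Such a subject would have peri-anal skin compared with peri-anal skin at 6 weeks and 6 months, and so would show nothing about the laser's effect on tissue. If that skin stays as it was, it pulls the average change towards zero. If it changes for another reason, the change is counted in a summary meant to describe lasered skin. The case is foreseeable, since Appendix II has an item for perianal involvement. The Protocol does not say how often peri-anal skin would be the most affected area.

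**Working it through.** The Protocol gives no figure to reproduce here, so the first step is textual.

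**Step 1. Is peri-anal skin inside the treated field?** Pre-Treatment Instructions item 5 names six sites under the vulva and does not introduce them as examples. The biopsy section sets peri-anal skin beside the vulva as an alternative, so it does not treat the first as part of the second. The synopsis and the device description also speak of the vulva. No section extends lasering to peri-anal skin.

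**Step 2. Does the biopsy rule require treated skin?** No. Its criteria are the appearance of disease, likely histological change, comfort and healing.

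**Step 3. Do other sections require it?** Table 2 and Follow-up Visits describe the biopsy as one of treatment or treated skin. A peri-anal sample would satisfy the biopsy section and depart from these two.

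**Step 4. How much could it matter?** This is an illustration on assumed values. It also assumes that histology is summarised as a mean change, which the Protocol does not state.

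- n = biopsied subjects, at most 10 (Table 2)
- m = subjects sampled only from skin that was not lasered (assumed; may be 0)
- f = change in that skin divided by change at lasered sites (assumed)

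Weight of one subject = 1/n: 1/10 = 10%, 1/8 = 12.5%, 1/5 = 20%.

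Pooled mean ÷ lasered-site mean = ((n − m) + m·f)/n.

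Share of the pooled change that comes from unlasered skin = m·f/((n − m) + m·f).

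| n | m | f | Pooled ÷ lasered-site mean | Share from unlasered skin |
|---|---|---|---|---|
| 10 | 1 | 0 | 9/10 = 90% | 0/9 = 0% |
| 10 | 1 | 0.5 | 9.5/10 = 95% | 0.5/9.5 = 5.3% |
| 10 | 1 | 1 | 10/10 = 100% | 1/10 = 10% |
| 10 | 2 | 0 | 8/10 = 80% | 0/8 = 0% |
| 10 | 2 | 0.5 | 9/10 = 90% | 1/9 = 11.1% |
| 10 | 2 | 1 | 10/10 = 100% | 2/10 = 20% |

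With m = 0 the pooled and lasered-site means are the same and nothing is lost.

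**The case against.** The best defence is to read the sections together. Table 2 and Follow-up Visits can be taken to limit the biopsy section, and a provider weighing likely histological change would naturally choose lasered skin. On that reading the defect is two loose words. This is a fair account of what many sites would do. It does not remove the conflict, because the only detailed instruction on site selection expressly admits peri-anal skin, and the other two places are short labels.

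It may also be said that the SAP or the CRFs already deal with this. Neither is shown, and which samples enter a summary is commonly left to the SAP. That is why the point rests on the conflict between protocol sections and not on a missing analysis rule. An SAP rule would still need the sub-areas to have been recorded.

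Four stronger readings are tempting, and the Protocol does not support them.

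- *One such subject accounts for a tenth of the observed change.* A subject among 10 has a tenth of the weight. The contribution to the change depends on f and is zero when f = 0.
- *The histology endpoint is invalid.* No section says that any subject will be biopsied peri-anally.
- *The primary endpoint is compromised by the biopsy rule.* The rule does not enter that endpoint. Appendix II does score perianal involvement, so one item of the primary assessment may concern skin that is not listed as lasered. That is a separate matter, but it means one should not say the treated-area question has no bearing on the primary endpoint at all.
- *Restricting the summary to lasered skin would make the change attributable to the laser.* There is a single group, and any topical corticosteroid is continued (Inclusion Criteria, item 5). Both affect lasered skin just as much.

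**Conclusion.** The inconsistency holds on the text. The biopsy section permits a sample from skin outside the listed treatment areas, the same-area rule carries that choice through all three time points, and two other sections describe the biopsy as one of treated skin.

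The consequence is small and conditional. It concerns one secondary endpoint in an optional subset of at most 10 subjects. If one of 10 were affected and that skin did not change, a mean change would be 90% of its value at lasered sites. With two of 10 it would be 80%. These figures rest on assumed values of m and f and on a mean being used. Confidence is high in the textual conflict and low in how often it would matter. Severity: minor.

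**What to change.** 1. Reconcile four places in the Protocol (Table 2, Vulvar Biopsy Procedure, Pre-Treatment Instructions item 5, and Follow-up Visits item 2) on whether biopsied skin must be treated skin. Which sites to treat or sample is for the sponsor and investigators, and this review takes no position on it.
2. If not already captured, record on the CRF the sub-area sampled at each biopsy and, for biopsied subjects, the sub-areas lasered at each treatment.
3. In the protocol or the SAP, base the change-from-baseline histology summary on samples from areas recorded as lasered, and list any others separately.

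The cost is wording in four places and two short CRF entries over up to eight visits (three biopsies plus up to five treatments). No biopsy, visit or procedure is added. The site is already told to "Mark the biopsy site with surgical skin marker and photograph the marked location", and treatment settings and response already go on the CRF. The drawback is that the histology summary may contain fewer subjects. The change removes dilution by unlasered skin. It does not supply the comparison group that attribution to the laser would need.
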